5.1.1 INCLUSION CRITERIA

- Patient admitted to Hospice at Home services
- Patient has a carer who also agrees to take part in the study
- Ability to obtain informed consent by any of the following
 - o Patient
 - o Carer/Relative/Friend
 - o Nominated consultee

5.1.2 EXCLUSION CRITERIA

- Inability to obtain consent from the participant (or a consultee)
- Patient without a suitable lay carer
- Patients in care homes at the time of admission to H@H service

5.2 CARER CONSENT

Carers will be invited to participate in the study when the person they are supporting or caring for is admitted to the H@H service. For the purposes of this study, the definition of a carer is someone close to the patient who provides care and support on a daily basis at home. This could be a family member, friend, partner or other person who fits this description. Carers should be approached at the same time as the patient. Local service staff e.g. registered nurses or health care assistants (or research nurse if they have one) will introduce the study and provide a carer information sheet. Once sufficient time has been allowed for participants to read the information and ask any questions they may have, the local service staff member will then gain their consent, using the study carer consent forms. A copy of the information sheet and consent form will be given to the carer and a copy filed in the study site file. After consent, the carer will be asked to complete a contact details form detailing the best telephone number to contact them on and the best day/time for the research team to call to collect data.

5.3 SERVICE PROVIDER AND COMMISIONER CONSENT

Service providers and Commissioners will be invited to undertake an in depth interview about the provision of H@H services. Potential participants will be invited by email or by telephone by the research team and an information sheet and consent form sent to them by email or post. If they

wish to take part, interviews will be arranged at a convenient time and location (either by telephone or in person) for the interviewee and will take no longer than 30 minutes. Prior to the interview, the participant will be asked to complete a consent form and return this to the research team.

6. DATA COLLECTION AND FOLLOW-UP

6.1 PATIENTS

After consent, a member of the participants direct care team will collect some background information about the patient, the Integrated Palliative Care Outcome Scale (iPOS) questionnaire (staff version), phase of illness and modified Karnofsky score. These data will be collected at the point of entry to the H@H service or within 24 hours of consent. The patient and carer pathway is laid out in Figure 2 below.

6.2 CARERS

After consent, a member of the research team will contact the carer as soon as possible to collect health service use data retrospectively for up to two months prior to recruitment. This data will be collected using the Ambulatory and Home Care Record (AHCR) that has been customised for use in this study (24). Contact will then be made on a fortnightly basis, by phone to collect prospective health service use data in the same way. This will take approximately 15 minutes every 2 weeks. The carer will be given a diary at the time of consent to be used as an aide memoire for fortnightly data collection telephone calls from the research team. The use of this diary is optional.

Post bereavement

Post-bereavement, a follow up letter will be sent to carers to remind them that the research team will be in touch to collect further data. This letter will include information sheets about the QODD questionnaire and also about the in-depth interview.

Questionnaire

Participants will be given options to do the QODD over the phone, using an online survey tool or by post. The following outcome data will be collected at up to two time-points: immediately post bereavement (optional, carer preference at last health resource data collection telephone contact); at around 1-6 months post bereavement:

- Quality Of Dying and Death (QODD) 7 day recall, Version 1
- 2 short questions about the overall care received

Where 3 attempts to contact the participating carer by telephone have been made with no success, a paper copy of the above follow up measures will be posted to the carer for completion on one occasion only. This will be accompanied by a cover letter to explain that the research team have been unable to contact them and/or if they would prefer to complete the questionnaire at home they can do so.

Optional interview

An in depth interview will be completed by a subset of participants only and will include semi-structured interview questions. We will initially interview approximately 20 per service model type with a stopping criterion of 3 interviews with no new themes coded in order to achieve data saturation (see qualitative data analysis) [25].

If the QODD is collected by telephone, the researcher will ask the participant if they would be willing to participate in an optional in depth interview by telephone or in person to understand more about the H@H service received.

If the QODD questionnaire is done in the postal or online form, carers can indicate if they would be happy to take part in an optional interview at the end of the questionnaire. If the postal or online QODD questionnaire is not completed within 1-2 months, a final follow up letter will be sent to ask carers to take part in the optional interview only. No further attempts will then be made to contact the carer by telephone unless carers indicate their willingness to take part in an interview in the postal/online QODD questionnaire or final follow up letter reply slip.

All study data will be collected by October 2019. Therefore, patients who are recruited and are still alive after 30 June 2019 will not be included in the study analysis.

[figure not shown]

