3. STUDY DESIGN

Our research design is informed by realist evaluation [16-17] that will be used to identify candidate programme theories that will be tested and refined throughout the proposed research in order to address our objectives. The funded programme of research will be conducted in 3 phases. This protocol outlines the research and processes for Phase 2 and subsequent Phase 3 consensus events (section 8.5).

Phase 1: Survey

A national telephone survey will be conducted of all known H@H services in the Hospice UK service directory to map the range and variation of H@H services in order to develop a typology of models. This phase has received HRA approval (HRA ref # 17/HRA/0299).

Phase 2: Case studies.

To ensure maximum range, we will purposively select up to 8 case studies of H@H services that vary in model 'type' and location (1-2 case studies per model). 66 patients per model type will be recruited and tracked over time (until death) through data collection from the service provider and the patient's

carer. The primary outcome will be the quality of death and will be collected post death. This will be collected using the Quality of Dying and Death (QODD) tool, a validated interview instrument conducted with bereaved carers [18-20]. Secondary outcomes will include holistic patient assessment (iPOS) [21] and assessment of care by bereaved relatives (VOICES) [22] and service use (AHCR) [23]. Regression analysis will be used to isolate the impact of each service model on quantitative outcomes. An embedded economic analysis will capture resource use and calculate costs. Barriers and enablers to service provision will be explored through in depth interviews with carers, commissioners and providers. Analysis will be iterative with the aim of testing and refining programme theories and to develop provisional context-mechanism-outcome (CMO) configurations. Normalisation Process Theory (NPT) [24] will be used to understand why a model has or has not been embedded within a whole system of care.

[figure not shown]
Phase 3: National consensus workshops.

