8.4 Economic analysis

The economic analysis will be at two levels. First, a descriptive analysis will be conducted of the resources and costs of running each case study H@H service. This will cover: staff; service facilities, equipment, overheads; transport for home care; other sundry items associated with care delivery. These data will be collected at interview with service managers. Where hospices provide community or inpatient services in addition to the H@H, guidance on appropriate attribution of costs will be sought from the finance manager. Information on activity rates will also be gathered so that costs per patient receiving H@H can be calculated and compared between case studies. Second, a patient level analysis will be undertaken. Due to the nature of this study, patients recruited will likely have short and variable life expectancy, leading to an inconsistent time horizon for the individual patient level data captured. This lack of a normalised time integrated measure of health outcome (such as a QALY) or cost, will make a traditional comparative cost -effectiveness analysis problematic. Hence, the economic analysis will be limited to a descriptive analysis of service utilisation and cost for the different H@H models. Whole system resource use in the end-of-life care will be captured prospectively from the point of recruitment to the study for each patient. At first interview, participants will be asked to report retrospectively, via recall, on service use for the two months prior to recruitment. Service utilisation data will cover primary, community, hospital, hospice, social care, voluntary and informal care received. A customised version of the Ambulatory and Home Care Record (AHCR) [23] will be used for this purpose.

Service use data, once captured, will be grouped into 4-6 time periods of approximately equal sample size, delimited by survival time following start of service use data collection. The cut points

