will be determined by the distribution of the data. In our previous study [9], 6% of patients referred to a H@H service had died within 2 days, 40% within one month, 62% within 2 months, and the remaining 38% were refer red over 2 months before death. Resource use will be converted to costs using national tariffs [32]. Informal care will be valued using replacement cost methods. For each of the model types of H@H service provision, an average cost/day of treatment will be estimated for the 4-6 time periods respectively. This will provide descriptive cost data, independent of expected survival time that can be compared between H@H model types. Alongside this analysis, a comparison of the average survival times for patients in each of the H@H models will be provided. However, caution will need to be taken when trying to infer a total cost of service from the survival data and average cost of service/day. Costs will be presented as means and median, given the typical skew in the distribution of costs. Comparison of costs between H@H model will be assessed for significance using Mann Whitney test. Sensitivity analysis for costs will be handled deterministically, varying the amount of resource use between their upper and lower limits for each H@H model type. Costs will be analysed in relation to outcomes from different models in a cost –consequences framework.

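### Removing every recruit alive after 30 June 2019 from the whole analysis right-truncates the survival times that section 8.4 compares between models

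*Protocol*

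**What the plan says.** All references are to the Phase 2 protocol; no SAP is shown.

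- **Section 6.2 (Carers)** gives the timetable, "All study data will be collected by October 2019", and draws from it the rule that "patients who are recruited and are still alive after 30 June 2019 will not be included in the study analysis". The rule is not limited to any one outcome.
- **Section 3 (Study design)** says that patients are followed until death and that the primary outcome, the QODD, is collected after death.
- **Section 8.4 (Economic analysis)** says that service-use data will be "grouped into 4-6 time periods of approximately equal sample size, delimited by survival time following start of service use data collection", with cut points that "will be determined by the distribution of the data". Within each model type, "an average cost/day of treatment will be estimated for the 4-6 time periods respectively". The protocol comments: "This will provide descriptive cost data, independent of expected survival time that can be compared between H@H model types". Alongside this, "a comparison of the average survival times for patients in each of the H@H models will be provided". No allowance for the cut-off is mentioned. Costs are to be compared by a Mann-Whitney test, without saying whether within bands or pooled over them.
- **Section 8.4** also gives survival from referral in the team's earlier study: 6% dead within 2 days, 40% within one month, 62% within two months, and 38% referred more than two months before death.

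**The concern.** Under the section 6.2 rule, a patient enters the analysis only if survival is no longer than the time between recruitment and 30 June 2019. That is right truncation. A patient recruited late is kept only if death comes quickly, while one recruited early is kept almost regardless of survival. A raw average over those kept is too short.

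The stated reason does not stretch as far as the rule. The October 2019 deadline explains why a QODD interview may be impossible for a patient still alive at the end of June. It does not explain discarding that patient's baseline data, survival to date or service use collected fortnightly from the carer. Section 6.4 lets data collected before a withdrawal be used, with the participant's agreement or where the participant cannot be asked. Section 6.2 discards equally valid data from patients who stayed in the study and lived.

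At stake is the survival comparison meant to accompany the cost-per-day results. It would mix survival with the recruitment calendar of each model's sites.

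**Working it through.** The protocol gives no figure for the share excluded or for mean survival. Its only relevant figures are the section 8.4 percentages, which are consistent: 62% + 38% = 100%.

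**Inputs**
- From section 8.4: cumulative deaths of 6% at 2 days, 40% at 30 days and 62% at 60 days, joined by straight lines.
- Assumed: beyond 60 days, an exponential tail with mean *m* of 30, 60 or 120 further days.
- Assumed: uniform recruitment from *b* to *a* days before the cut-off, with 30.4 days to the month.

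**True mean.** This is the area under the survival curve S(t):
- 0-2 days: 2 × (1 + 0.94)/2 = 1.94
- 2-30 days: 28 × (0.94 + 0.60)/2 = 21.56
- 30-60 days: 30 × (0.60 + 0.38)/2 = 14.70
- beyond 60 days: 0.38*m*

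The total is 38.2 + 0.38*m*, or 49.6, 61.0 and 83.8 days for *m* = 30, 60 and 120.

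**Share excluded** = ∫S(u)du from *a* to *b*, divided by (*b* − *a*). Two examples:
- Six months up to the cut-off, *m* = 120: [38.2 + 45.6 × (1 − e^(−122.4/120))]/182.4 = 67.4/182.4 = 36.9%.
- From 9 to 3 months before, *m* = 120: 45.6 × (e^(−31.2/120) − e^(−213.6/120))/182.4 = 15.1%.

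**Mean among those kept** = ∫[∫₀ᵘS(t)dt − u·S(u)]du / ∫[1 − S(u)]du, with the outer integrals from *a* to *b*.

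| Recruitment, months before cut-off | Excluded (*m* = 30 / 60 / 120) | Kept mean ÷ true mean |
|---|---|---|
| 18 to 0 | 9.1 / 11.1 / 15.2% | 0.94 / 0.88 / 0.72 |
| 12 to 0 | 13.6 / 16.7 / 22.0% | 0.90 / 0.80 / 0.60 |
| 6 to 0 | 27.1 / 31.8 / 36.9% | 0.77 / 0.61 / 0.40 |
| 18 to 3 | 0.9 / 3.0 / 7.5% | 0.98 / 0.92 / 0.77 |
| 9 to 3 | 2.2 / 7.1 / 15.1% | 0.95 / 0.82 / 0.58 |
| 18 to 6 | 0.1 / 0.8 / 4.3% | 1.00 / 0.97 / 0.83 |
| 12 to 6 | 0.1 / 1.5 / 7.0% | 1.00 / 0.94 / 0.74 |

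**Two models with identical survival.** If one recruits for 18 months and the other for 6, both up to the cut-off, the kept means are 46.5 v 38.4, 53.4 v 37.1 and 60.6 v 33.7 days. The spurious differences are about 8, 16 and 27 days. With 18- and 9-month starts, both stopping three months early, the difference is about 1 to 16 days.

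**Other survival shapes.** Weibull (shape 0.86, scale 64.4 days) and log-normal (sigma 1.58, median 40.9 days) curves fitted to the same percentages give 56 v 35 and 56 v 31 days for 18 v 6 months up to the cut-off. With 66 recruits per model, a Mann-Whitney test on survival, used only as a yardstick, rejects equality in about 33% of runs instead of 5%. For 18 v 12 months it rejects in 6-7%. The log-normal tail is heavier: an 18-month start with recruitment stopped six months early still excludes about 9%.

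**Cost per day.** The cost curve is assumed for illustration: 300 per day in the last 14 days of life and 60 per day before. Spurious differences between models with identical survival and costs, under the two fitted curves, are:

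| Recruitment windows up to cut-off | Closed bands (4 or 6 bands) | Open top band | Pooled over bands |
|---|---|---|---|
| 18 v 6 months | at most 0.6% | 7-10% | about 13% |
| 18 v 9 months | at most 0.4% | 3-5% | about 7% |
| 18 v 12 months | at most 0.2% | 1-3% | 3-4% |

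**The case against.** **Cost per day.** A reader might infer that the whole cost comparison is biased. The documents do not support that. Section 8.4 bands patients by observed survival, and among patients who died after a given time the cut-off does not change what their days cost. The closed bands confirm this. What remains is the open longest-survival band, cut points taken from a truncated distribution, and any test pooled over bands, which section 8.4 neither specifies nor rules out.

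**Size.** A reader might take 37% excluded, or a kept mean of 0.40 of the truth, as the expected effect. Those figures need a late six-month window ending at the cut-off and a long tail. No recruitment start or stop date is given, and an early stop makes the loss small. The percentages also run from referral in an earlier study, not from recruitment in this one.

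**Spurious contrasts.** A reader might infer that equal models will appear different. That requires unequal recruitment calendars. Site-by-site assessment (section 9.1) and adding sites to reach 66 patients (section 8.1) make this plausible, but the protocol does not say it will happen. With equal calendars there is no spurious contrast; survival is still understated and true differences are generally attenuated.

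**Primary outcome.** For the QODD the exclusion is inherent, because the instrument is completed after death. A reader might add that the QODD sample then falls short of the 44 per model required in section 8.1. That depends on whether the 33% allowance covers these patients, which the protocol does not say.

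**Standing of the analysis.** Section 8.4 calls the economic analysis descriptive, names no test for survival, and urges caution in deriving total cost from survival and cost per day. Estimation methods may sit in a SAP. This lowers the severity. It does not remove the point, because the protocol itself fixes both the exclusion and the averages computed after it.

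**Conclusion.** The point holds for the survival comparison. The rule reaches further than its reason, and the averages in section 8.4 are right-truncated as written. They are too short in every model, by an amount that follows the recruitment calendar and can differ between models.

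Under the piecewise-linear curve with a 30- to 120-day tail mean, exclusion is:
- about 9-37% if recruitment runs to the cut-off over 6 to 18 months, with kept means 0.94 down to 0.40 of the truth;
- about 1-15% if it stops three months earlier (starts 9 to 18 months before the cut-off);
- about 0.1-7% if it stops six months earlier (starts 12 to 18 months before).

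These ranges rest on uniform recruitment, the assumed tail, and survival from recruitment resembling survival from referral in the earlier study. The claim that cost data are independent of expected survival is safe for closed bands. It is not safe for the open top band or for pooled costs.

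This should be corrected before analysis. It is an error in a descriptive secondary analysis and does not undermine the primary comparison.

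**What to change.** 1. **Section 6.2:** limit the exclusion of patients alive after 30 June 2019 to the QODD and other post-bereavement outcomes. Keep all recruits in the baseline tables.
2. **Section 8.4, survival:** censor living recruits at 30 June 2019 and report Kaplan-Meier medians or restricted mean survival by model in place of raw averages. Applying the present rule already requires knowing who was alive on that date. Censoring at a fixed date also assumes that survival did not drift over the recruitment period.
3. **Section 8.4, costs:** keep survivors' service use up to the cut-off. Place them in a band only where it is already known, for example the open top band once they have passed its lower limit, and report the rest separately. Their observed days omit the end of life, so show the top band with and without them. State whether the Mann-Whitney test is run within bands or pooled.
4. **Reporting:** give, by model, recruitment start and stop dates and the number left out of the QODD as alive.

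The cost is rewording two sections and modest extra analysis. It needs no new data collection.

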6.3 SERVICE PROVIDERS AND COMMISIONERS

The central research team will conduct semi-structured interviews with 5-10 managers, healthcare staff and commissioners per case study site. This may include local supporting service providers e.g. district nurses, who will be identified by the case study sites. Interview schedules will contain semi-structured questions to explore the service logic, rationale, processes and contextual features facilitating or inhibiting service delivery, as well as enablers and barriers to providing H@H services. Service providers and commissioners will be approached as soon as possible after local study approvals have been granted for an initial interview. One to two interviewees will be invited to undertake a follow up interview during the last 6 months of data collection (between Jan 2019 and July 2019) to understand any changes to the service over the course of the study. The same interview guides will be used for both initial and follow up interviews.

6.4 WITHDRAWAL CRITERIA

Participants will be free to withdraw from the study at any time. Patients are made aware that this will not affect the care they receive in the patient information sheet. If a participant withdraws from the study, where possible, they will be asked if the data collected to date may still be used in the final analysis. If they do not wish for their data to be used in this way, all data collected from the participant will be destroyed. If it is not possible to consult the participant on this, data collected up to the point of withdrawal will be used according to the original consent.

Figure 2: Study patient and carer pathway

7. ADVERSE EVENTS

Adverse Event (AE): any untoward medical occurrence in a patient or clinical study subject.

As this study involves no clinical intervention, AE's are not expected. Due care and attention will be taken when collecting data from patients and carer in order to avoid distress or fatigue. In order to identify and support distressed participant, researchers will follow the study Distress Protocol (see Appendix 1) at all times.

Where an adverse event is deemed to be a result of a research activity (namely patient or carer consent or data collection), it will be reported to the Study Co-ordinator. Any questions concerning adverse event reporting should be directed to the Study Co-ordinator in the first instance. The Chief Investigator will notify the Sponsor of all relevant AEs.

If participants wish to make a complaint, they have been provided with contact details to do so in the patient information sheet.

